#### Protections Against Risk:

To minimize risk, all procedures will be performed in clinically stable participants who meet eligibility criteria under the direct supervision of the principal investigators and other research personnel with appropriate training and licensure. All study procedures are performed at the NYU Clinical Translational Science Institute Clinical Research Center located within Bellevue Hospital with immediate access to emergency support equipment and personnel in the event of deterioration in clinical status.

Participant risks are also minimized by the following protections described in the study protocol:

- Study entry criteria to exclude potential participants at greater risk of adverse events
- Administration of ferumoxytol injection according to the FDA-approved prescribing information
- Active monitoring for potential treatment related adverse effects and other adverse events
- Pre-specified criteria for participant withdrawal to protect participant safety
- Pre-specified criteria for study termination or suspension to protect participant safety

CONFIDENTIAL

This material is the property of the NYU School of Medicine and Langone Medical Center. Do not disclose or use except as authorized in writing by the study sponsor  
Interventional Template Version: 28 APR 2017

It is important to note that VAD patients with iron deficiency not enrolled in this study will be referred for standard of care treatment with other FDA-approved intravenous iron formulations that have comparable safety profiles to ferumoxytol injection. Accordingly, the risks related to drug infusion during participation in this study are no different than risk related to standard of care, and may actually be lower since ferumoxytol requires only two infusions, whereas other commonly used preparations require 5-6 infusions.

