### **5.7 Participant Withdrawal or Termination**

#### **5.7.1 Reasons for Withdrawal or Termination**

CONFIDENTIAL

This material is the property of the NYU School of Medicine and Langone Medical Center. Do not disclose or use except as authorized in writing by the study sponsor  
Interventional Template Version: 28 APR 2017

Participants are free to withdraw from participation in the study at any time upon request. An investigator may terminate participation in the study if:

- Any clinical adverse event (AE), laboratory abnormality, or other medical condition or situation occurs such that continued participation in the study would not be in the best interest of the participant
- The participant meets an exclusion criterion (either newly developed or not previously recognized) that precludes further study participation
- The participant is not able to return for the second dose of ferumoxytol within 15 days of the first dose.

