### **5.7.2 Handling of Participant Withdrawals or Termination**

Withdrawn or terminated participants will be followed for extraction of clinical data from the medical record for 6 months with participant permission. Since the primary outcome is feasibility, there will be no replacement of withdrawn subjects.

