# **7 Study Procedures and Schedule**

## **7.1 Study Procedures/Evaluations**

### **7.1.1 Study Specific Procedures**

Study visits (See Attached Study Schematic Figure and Schedule of Assessments Table): The study will require 3 visits over approximately 2 weeks for each subject.

- Visit 1: Informed consent and screening\*
- Visit 2: First dose of ferumoxytol injection Study Drug\*
- Visit 3: Second dose of ferumoxytol injection Study Drug

\*Visits 1 and 2 may occur on the same day.

Screening procedures. After the informed consent form is signed, chart review and patient interview will be performed to determine eligibility. Screening will include subject interview and chart review to determine eligibility. Clinical information on co-morbid conditions, VAD settings, and concomitant medications will be collected. Vital signs in the seated position and a brief cardiovascular exam will be recorded. Women of childbearing potential will undergo urine or blood pregnancy testing.

Study Drug Administration: Ferumoxytol injection will be administered to eligible subjects according to FDA-approved prescribing information. Prior to administration, interim history, concomitant medications, VAD settings, vital signs and a cardiovascular exam will be recorded. Two doses of ferumoxytol injection will be administered: an initial 510 mg dose followed by a second 510 mg dose 3 to 8 days later, each dose given as an intravenous infusion in 50-200 mL 0.9% Sodium Chloride Injection, USP or 5% Dextrose Injection, USP while the subject is in a reclined or semi-reclined position. Subjects will be observed for signs or symptoms of hypersensitivity reactions (including monitoring of blood pressure and pulse rate) during and for at least 30 minutes after ferumoxytol injection administration. The dose, date and time of infusion, duration of infusion, and treatment-related adverse effects (diarrhea, nausea, dizziness, hypotension, hypersensitivity) will be recorded.

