#### **7.3.1 Screening**

##### **Screening Visit (Visit 1, Day -14 to 0)**

- Obtain informed consent of potential participant verified by signature on written informed consent for screening form.
- Review medical history to determine eligibility based on inclusion/exclusion criteria.
- Record concomitant medications
- Record VAD settings, seated vital signs (mean blood pressure, heart rate, oxygen saturation) and cardiovascular examination.
- Schedule study visits for participants who are eligible and available for the duration of the study. If the participant is eligible to receive Ferumoxytol injection, the first administration of study drug may be completed on the same day as the screening visit.
- Obtain urine or blood pregnancy test in women of child-bearing potential.
- Provide participants with instructions for the return for the infusion of Ferumoxytol injection .

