## **9.2 Statistical Hypotheses**

Primary Feasibility Objective: The null hypothesis for the primary feasibility objective is that 75% of the subjects will successfully complete ferumoxytol injection treatment as per study protocol.

CONFIDENTIAL

This material is the property of the NYU School of Medicine and Langone Medical Center. Do not disclose or use except as authorized in writing by the study sponsor  
Interventional Template Version: 28 APR 2017

There are no hypotheses to be tested for the primary safety objective and exploratory secondary objectives. Descriptive statistics will be used to analyze these data. The purpose of the analyses is to obtain estimates of the study treatment risk in the study population, and the magnitude and variance of change in the exploratory endpoints in the study population. These pilot data will be useful for planning of future clinical trials.

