### **9.3 Analysis Datasets**

Feasibility analysis dataset. Intention to treat (ITT) will be defined as all patients who provide consent and are eligible to receive study treatment. The ITT data set will be used for the primary feasibility endpoint.

Safety objective and exploratory objectives analysis dataset. All eligible subjects who received any study drug, and for whom post-dose data are available, will be included in the safety and exploratory objectives analysis set.

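### Section 9.3 requires participants in the safety set to be eligible as well as treated, without defining the word, so a dosed participant with a late-discovered exclusion can be left out of the adverse event incidence

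*Combined protocol and SAP*

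**What the plan says.** Section 9.3 defines one set for both the safety and the exploratory objectives: "All eligible subjects who received any study drug, and for whom post-dose data are available". That sets three conditions: eligible, treated, and with data after dosing. The set serves the primary safety endpoint in section 9.4.1, the incidence of treatment-related adverse events. No separate all-treated set is defined.

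Section 5.7.1 lists this among the grounds on which the investigator may end participation: "The participant meets an exclusion criterion (either newly developed or not previously recognized) that precludes further study participation". Section 5.7.2 adds: "Since the primary outcome is feasibility, there will be no replacement of withdrawn subjects". Terminated participants are still followed through the medical record for six months, with their permission.

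On how eligibility is settled, section 7.1.1 says "Screening will include subject interview and chart review to determine eligibility", and the screening visit in section 7.3.1 says "Review medical history to determine eligibility based on inclusion/exclusion criteria". The criteria are checked again at Visit 2 before the first dose and at Visit 3 before the second (sections 7.3.2 and 7.3.3).

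Section 9.2 gives the aim of the safety analysis: "The purpose of the analyses is to obtain estimates of the study treatment risk in the study population".

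**The concern.** A safety set normally rests on exposure. Adding eligibility makes membership depend on something that can be learned after dosing. A participant whose exclusion was present but unrecognized when the first infusion was given was exposed to the drug, yet on a literal reading was never an eligible subject. No other section returns that person to the safety analysis.

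The direction of any error is also a concern. Under Protections Against Risk in section 2.4.1, the plan lists among its safeguards "Study entry criteria to exclude potential participants at greater risk of adverse events". If the criteria work as intended, those dosed despite an exclusion are more likely than others to have an event, so leaving them out would tend to lower the reported incidence. This is clearest for a missed history of anaphylaxis or of hypersensitivity to intravenous iron. It is less clear for exclusions such as a recent hospitalization, because the endpoint counts treatment-related events only.

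The estimate is meant to guide later trials (section 3), and section 2.1 states that there are no published data on ferumoxytol in this population. With 20 participants and no replacement, one person moves the incidence by about five percentage points.

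**Working it through.** **Inputs.** The documents give 20 participants (section 5.6), no replacement of withdrawn subjects (section 5.7.2) and the set definition (section 9.3). The event counts below, and the condition that all 20 are dosed, are assumptions for illustration. The plan states no figure for the safety endpoint that could be reproduced. Its one power figure concerns feasibility and does not depend on the safety set.

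**Step 1: which condition can remove someone?** Every participant is observed "during and for at least 30 minutes after ferumoxytol injection administration", so nearly everyone dosed will have some post-dose data. The word eligible is the condition that can remove an exposed person.

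**Step 2: effect of omitting one participant.** Let x be the number with a related event among n analysed. The incidence is x/n. The exact (Clopper-Pearson) 95% interval runs from the 0.025 quantile of Beta(x, n-x+1) to the 0.975 quantile of Beta(x+1, n-x), with a lower limit of 0 when x = 0.

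| Omitted participant | All dosed | Omitted from the set |
|---|---|---|
| Had the only event | 1/20 = 5.0% (0.1-24.9%) | 0/19 = 0% (0-17.6%) |
| Had one of two events | 2/20 = 10.0% (1.2-31.7%) | 1/19 = 5.3% (0.1-26.0%) |
| Had one of three events | 3/20 = 15.0% (3.2-37.9%) | 2/19 = 10.5% (1.3-33.1%) |
| Had no event; one event elsewhere | 1/20 = 5.0% | 1/19 = 5.3% |

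The change matters only when the omitted person had a related event.

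**Step 3: how often could this happen?** The documents give no rate of missed exclusions. Let q be the assumed proportion of dosed participants with one, and e the assumed proportion with a related event, taken as independent of eligibility.

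- At least one of 20 has a missed exclusion: 1-(1-q)^20. For q = 0.01, 0.02 and 0.05 this is 0.182, 0.332 and 0.642.
- At least one of 20 has both a missed exclusion and a related event: 1-(1-qe)^20. For (q, e) = (0.01, 0.05), (0.02, 0.10) and (0.05, 0.20) this is 0.010, 0.039 and 0.182.

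These ranges, 18-64% and 1-18%, are upper bounds on removal at the assumed rates. They treat every missed exclusion as later discovered, and one that is never discovered removes nobody. They apply only under the literal reading. The second range also rests on independence; if related events are more common among those with a missed exclusion, the bound would be higher.

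**The case against.** The strongest answer is that the protocol generally treats eligibility as settled before dosing. Section 7.1.1 has the drug given to eligible subjects, section 7.3.1 allows same-day dosing once a participant is eligible, section 7.3.2 verifies the criteria before the first dose, and the feasibility set in section 9.3 itself speaks of being eligible to receive treatment. On that usage an eligible subject who received drug is simply someone cleared and dosed, and nobody is removed in retrospect. Section 5.7.1 concerns ending participation at the investigator's discretion and does not govern analysis sets. This stands as a reasonable reading. It does not close the point, because no section adopts it and the literal reading remains open.

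It is also fair to say that a high rate of missed exclusions is doubtful. Participants come from one program of 40-50 patients followed by a dedicated team, and some exclusions, such as hemodialysis or mechanical ventilation, could hardly be overlooked. The upper end of the assumed rates should be read with that in mind.

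Two stronger inferences are tempting but not supported. A reader might infer that someone who first develops an exclusion after dose 1, such as a hypersensitivity reaction, drops out at the Visit 3 check. That participant met the criteria when dosed and is best read as still eligible. A reader might also infer that events would go unrecorded or that safety oversight is weakened. Section 8.3 requires all on-study adverse events to be documented, section 8.4 governs reporting to the IRB, and the halting rule in section 8.6 does not refer to an analysis set.

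**Conclusion.** The wording is a real but minor defect. On a literal reading a dosed participant with a late-discovered exclusion can be left out of the primary safety endpoint; the documents do not establish that such a participant must be. The ambiguity is itself the problem: in an open-label trial, the meaning of the word could be chosen with the events in view.

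If one such participant had a related event, the reported incidence would fall by about five percentage points, from 5.0% to 0% where it was the only event. This assumes all 20 are dosed and only one is omitted. The intervals are wide and overlap heavily, the endpoint is descriptive with no hypothesis test, and the likelihood cannot be derived from the documents. The consequence is limited to the published incidence and what later trials take from it.

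**What to change.** In section 9.3, define the safety set as all participants who received any amount of study drug, regardless of what is later found about their eligibility. Keep the post-dose-data condition for the exploratory endpoints only. If the eligible-only incidence is of interest, show it as a supplementary line.

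The cost is a wording amendment to one section and IRB review. It needs no new data, visits or participants: adverse events are already documented for everyone on study, and terminated participants are already followed by chart review with permission. Sample size, power and alpha are unchanged. Section 7.3.3 needs no change.

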## **9.4 Description of Statistical Methods**

### **9.4.1 General Approach**

This is a single-arm open label study with a primary feasibility outcome. Descriptive statistics will be used to summarize pertinent characteristics of the study population.

Study Endpoints:

Primary Feasibility Endpoint: The proportion of eligible subjects who complete ferumoxytol injection therapy per study protocol.

Primary Safety Endpoint: The incidence of treatment-related adverse events

Other Exploratory Endpoints:

- Change from pre-treatment baseline in serum ferritin 2-24 weeks after ferumoxytol injection therapy
- Change from pre-treatment baseline in transferrin saturation 2-24 weeks after ferumoxytol injection therapy
- Change from pre-treatment baseline in hemoglobin level 2-24 weeks after ferumoxytol injection therapy
- Change from pre-treatment baseline in 6-minute walk distance 2-24 weeks after ferumoxytol injection therapy

### **9.4.2 Analysis of the Primary Efficacy Endpoint(s)**

Chi-Square analysis will be used to compare the observed proportion of successful completion of ferumoxytol injection treatment with the null hypothesis of 0.75. Statistical significance will be inferred for one-tailed p-value <0.05.

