### **5.6 Total Number of Participants and Sites**

Recruitment will end when 20 participants are enrolled. It is expected that 20 participants will be enrolled in order to produce 20 evaluable participants.

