#### **9.5 Sample Size**

The null hypothesis for the primary feasibility objective is that 75% of the subjects will successfully complete ferumoxytol injection treatment as per study protocol. 20 subjects will provide >80% power (one-tailed alpha=0.05) to detect <40% successful completion of ferumoxytol injection treatment.

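### The large-sample chi-square test of completion against 0.75 should be an exact binomial test: it understates p near the decision boundary and can exceed 5% error if the ITT number is not 20

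*Combined protocol and SAP*

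**What the plan says.** Section 9.4.2 sets the primary analysis: "Chi-Square analysis will be used to compare the observed proportion of successful completion of ferumoxytol injection treatment with the null hypothesis of 0.75". It adds: "Statistical significance will be inferred for one-tailed p-value <0.05". The Statistical Analysis row of the Protocol Summary says the same. Neither place says whether the test is exact or asymptotic, whether a continuity correction applies, or how a one-tailed p-value is taken from a chi-square statistic.

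The direction comes from section 9.5, and from the same statement in the Protocol Summary: "20 subjects will provide >80% power (one-tailed alpha=0.05) to detect <40% successful completion of ferumoxytol injection treatment". The alternative lies below the null, so the test is lower-tailed.

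Three places govern the denominator.

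- Section 9.3: the ITT set, used for the primary endpoint, is "all patients who provide consent and are eligible to receive study treatment".
- Section 5.6: "Recruitment will end when 20 participants are enrolled".
- Sections 7.3.1 and 7.3.2: consent is taken at Visit 1, up to 14 days before Visit 2, and Visit 2 carries the enrolment and baseline label.

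Section 9.2 confirms that no hypothesis is tested for the safety or exploratory objectives, so this is the only test in the trial.

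**The concern.** The chi-square p-value rests on a normal approximation to a binomial count. At 20 subjects the expected number of non-completers under the null is 20 × 0.25 = 5, the usual rule-of-thumb minimum. The null proportion is also well away from one half, so the distribution is skewed towards low counts. In that setting the approximation makes the lower tail look thinner than it is, and p comes out too small.

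Two things are at stake. The first is the reported p-value, which can be wrong by about a factor of two close to the boundary even when the decision is right. The second is the decision itself. The chi-square and exact rules agree at 20, but agreement depends on the exact number analysed, and the plan does not fix that number at 20.

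**Working it through.** **Inputs.** Null completion p0 = 0.75, alternative 0.40, one-tailed alpha 0.05 and N = 20 (section 9.5); chi-square test (section 9.4.2); ITT denominator (section 9.3). The actual ITT number is not in the documents, so values around 20 are assumed and shown as a range.

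**The plan's own figure.** The exact lower-tail test at N = 20 rejects at 11 or fewer completers.

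- Size: P(X ≤ 11 | 20, 0.75) = 0.0409. The next cut-off, 12, would give 0.1018.
- Power: P(X ≤ 11 | 20, 0.40) = 0.943.

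The stated power of more than 80% is therefore met with room to spare.

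**The p-value at N = 20.** The signed root of the uncorrected chi-square is z = (x − N·p0) / √(N·p0·(1 − p0)), and halving the chi-square p gives Φ(z) for x below 15. At x = 11:

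- z = (11 − 15) / √3.75 = −2.066, so chi-square = 4.267
- chi-square p = 0.0389, halved 0.0194
- exact lower-tail p = 0.0409, a ratio of 0.0194 / 0.0409 = 0.47
- with continuity correction, Φ((11.5 − 15) / √3.75) = 0.035

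| Completers of 20 | Halved chi-square p | Exact p | Ratio |
|---|---|---|---|
| 10 | 0.0049 | 0.0139 | 0.35 |
| 11 | 0.0194 | 0.0409 | 0.47 |
| 12 | 0.0607 | 0.1018 | 0.60 |
| 13 | 0.151 | 0.214 | 0.70 |

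The factor of about two belongs to the boundary and is not constant.

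**True error by ITT number.** For each N, find the largest count c with Φ(z) < 0.05, then compute P(X ≤ c | N, 0.75). Compare it with the exact test's own cut-off.

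| N | Chi-square rejects at | True error | Exact rejects at | True error | Exact power at 40% |
|---|---|---|---|---|---|
| 17 | ≤ 9 | 4.0% | ≤ 9 | 4.0% | 90.8% |
| 18 | ≤ 10 | 5.7% | ≤ 9 | 1.9% | 86.5% |
| 19 | ≤ 11 | 7.7% | ≤ 10 | 2.9% | 91.2% |
| 20 | ≤ 11 | 4.1% | ≤ 11 | 4.1% | 94.3% |
| 21 | ≤ 12 | 5.6% | ≤ 11 | 2.1% | 91.5% |
| 22 | ≤ 13 | 7.5% | ≤ 12 | 3.0% | 94.5% |
| 23 | ≤ 13 | 4.1% | ≤ 13 | 4.1% | 96.5% |

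**A result on which the decision changes.** With 13 of 22 completing, z = (13 − 16.5) / √4.125 = −1.723. The halved chi-square p is 0.042 (reject); the exact p is 0.075 (do not reject).

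**Why N may differ from 20.** If enrolment happens at Visit 2, a patient who consents, is found eligible and never reaches Visit 2 belongs to the ITT set but does not count towards the 20 at which recruitment stops. That mechanism pushes N above 20 only. Values below 20 would need a recruitment shortfall. Section 5.4 gives a source population of 40 to 50 patients, but the documents do not predict a shortfall.

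**The case against.** The strongest reply is that nothing changes at the planned size. At 20 the two tests share a rejection region, the error is 4.1%, the power statement is sound, and no go/no-go action is tied to the p-value in what is a pilot. All of that stands. Section 5.6 also expects 20 enrolled to yield 20 evaluable, and section 5.5 allows screening and first dose on one day, which narrows the gap between consent and enrolment. The Visit 2 label is not decisive either, since section 7.3.3 puts the same label on Visit 3.

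A second reply is that the excess depends on a version of the test that the plan does not name. This also stands. With a continuity correction, the rejection region equals the exact one at every N from 14 to 23. With the chi-square p left unhalved, it does so from 14 to 26. The uncorrected, halved form is the usual reading of a one-tailed chi-square rule, but it is a reading.

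Two stronger inferences should be resisted. A reader might infer that the test has no direction, because 11 of 20 and 19 of 20 give the same chi-square, so that near-perfect completion could be declared significant. The documents do not support this: section 9.4.2 requires a one-tailed p-value, and section 9.5 and the Protocol Summary place the alternative below 40%. Section 9.4.2 merely fails to repeat the tail. A reader might also infer that error exceeds 5% whenever N is not 20; N = 17 and 23 show otherwise.

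**Conclusion.** The point holds in limited form. The named test is a poor choice at this size. In its usual uncorrected, halved form it reports 0.019 where the exact value is 0.041 at the N = 20 boundary. If the ITT number reaches 21 or 22, which the definitions permit, its true error is 5.6% or 7.5%. If recruitment fell short, an assumption with no support in the documents, 18 and 19 would give 5.7% and 7.7%. At exactly 20, only the reported p-value is affected.

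The conclusion rests on the uncorrected, halved version of the test, a lower-tail alternative, and an ITT number that can differ from 20. The sample size and its power claim are not in question. A change is worth making because the exact test holds error at or below 5% at any number and keeps power at 40% completion above 86% from 18 to 22.

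**What to change.** In section 9.4.2 and the Protocol Summary, replace the chi-square test with an exact binomial test of 0.75 on the actual ITT number. Name the lower tail, to match section 9.5. Report the completion proportion with a Clopper-Pearson 95% confidence interval; 11 of 20, for example, gives 55% with an interval of 32% to 77%. For a pilot meant to inform later trials, that interval will be more useful than the test.

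The cost is one sentence in each place. Sample size, visits and data collection do not change. The one visible consequence is a larger p-value near the boundary (0.041 in place of 0.019 at 11 of 20), which is the correct one.
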